- Another randomized trial suggests that a live call the day prior to the procedure can increase the adequacy of the bowel prep.

PROJECT QUESTIONS AND HYPOTHESES

This project will address the following question:

Does an “enhanced” IVR-T protocol differ in effectiveness from the standard IVR-T protocol in reducing missed appointments and late cancellations for GI endoscopy?

Hypothesis 1: The enhanced IVR-T protocol will be more effective.

RESEARCH DESIGN AND METHODS

We will conduct a randomized trial over a 6-month period (March through September 2019) in the 3 GI endoscopy clinics (Franklin, Rock Creek, and Lone Tree). All members currently receive a text reminder 7 days prior to their procedure, which rolls over to a telephone reminder if the text cannot be delivered or the member’s phone is not text-enabled. Members will be randomized either to receive this standard IVR-T protocol or to receive an enhanced reminder protocol.

Inclusion criteria:

- a. Members scheduled for any GI procedure (upper endoscopy, colonoscopy, or both), with or without anesthesia, at all three clinical sites (Franklin, Rock Creek, Lone Tree) will be included if their procedure is scheduled \geq 2 days prior to the procedure. The IVR-T protocol will be adapted based on the wait time between appointment scheduling and the date of the procedure.
- b. Members with all clinical indications (screening, diagnosis, or surveillance), will be included.

Exclusion criteria:

- a. KPCO members who request not to participate in research or not to receive IVR-T or email outreach
- b. KPCO members in the “break the glass” or “code pink” protocols.
- c. Members whose procedure is scheduled $<$ 2 days prior to the procedure.

Randomization: Beginning in March 2019 (or on completion of all necessary design steps), we will use the randomization algorithm in the Structured Query Language program that manages the IVR relational database to assign each visit for a procedure at all three sites to one of the two interventions. Since members with multiple procedures on different days during the study period could receive different interventions for different visits, we will limit the statistical analysis to the first randomized appointment during the project period. Randomization will be stratified by clinic site.

Intervention content

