- For the duration of this intervention, the GI clinic will discontinue all live pre-procedure reminders so that we can assess the effectiveness of a purely automated intervention. Staff will continue post-procedure calls to assess service quality. Selective live reminders for members at high risk of missed appointments will be assessed in Step 3 of this project.

Intervention delivery: All interventions by email, text and telephone will be delivered by secure messages from the Automated Communication Technology (ACT) team in the KPCO

Institute for Health Research. At present, GI clinic nurses or staff make live reminder calls to some members as time allows; these calls will be stopped for the duration of the Step 1 trial.

Over the 6-month period of the project, we estimate that approximately 2300 visits per month will be scheduled across the 3 participating sites. After anticipated exclusions (10% of total cases), we estimate that there will be approximately 2100 eligible appointments per month. We project that the study will run from March 8, 2019 through September 7, 2019 to achieve the proposed sample size of approximately 13,000 appointments. The duration of the study will be dictated by the number of appointments necessary to detect an operationally significant reduction in the rate of appointment loss, as described in the sample size calculations below. We will monitor recruitment during the study and adjust the duration of the randomization period as necessary to achieve the projected sample size.

9. Study Measures

Outcome variable: The primary outcome for the study will be “appointment loss”, defined by GI leaders as the combined rate of prior day cancellations, same-day cancellations, and missed clinic appointments (“no shows”). The rationale for this outcome definition is that it is difficult to schedule new procedures within this time frame. As a secondary outcome, we will assess the adequacy of the bowel preparation for colonoscopy only.

Covariates: To describe the project participants and identify clinically and operationally relevant subgroups, we will measure patient covariates that we have used in prior IVR-T evaluations in primary care clinics, as well as variables specific to the GI clinic setting. These variables are listed in Appendix 1. All variables will be drawn from the IHR Virtual Data Warehouse (VDW), KPCO appointment scheduling system, or endoscopy data from Clarity.

10. Sample size and statistical analysis

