Sample size calculation: As shown in Table 1, “appointment loss” in the 3 GI clinics has been 6.8% from January – mid-October 2018. Across sites, approximately 2580 procedures/month were scheduled, and 175 were missed. Using standard parameters for Type 1 error (0.05, two-sided) and Type 2 error (0.20), the necessary sample to detect differences between standard and enhanced IVR-T protocols is:

Table 3. Sample Size Estimates

Detectable difference in appointment loss	N total (per group)	Duration of project (months)
3% absolute difference (6.8% vs. 3.8%)	2654 (1327)	1.3
2% absolute difference (6.8% vs. 4.8%)	5644 (2822)	2.7
1% absolute difference (6.8% vs. 5.8%)	21244 (10622)	10.1
20% relative difference*	11112 (5556)	5.3

(6.8% vs. 5.4%)		
-----------------	--	--

*Effect consistent with prior KPCO trials and systematic reviews of missed appointment interventions

Based on these calculations, a 6-month study will provide statistical power to detect a 20% relative difference in appointment loss.

Analytic plan Statistical analyses will be consistent with approaches used in prior IVR-T interventions. Patient demographic and clinical characteristics will be compared between the 2 groups using *t*-tests for normally distributed continuous variables, Wilcoxon rank tests for non-normally distributed continuous variables, and chi-square tests for discrete variables. We will assess the effectiveness of the intervention across the 3 participating clinics, after adjusting for predictors of missed appointments/late cancellations. To estimate the number of additional kept visits and available appointments per week that would result if the most effective intervention were implemented for all visits that met inclusion criteria, we will multiply the average number of visits at each clinic by the sum of the rate reduction in missed appointments and the rate increase in cancelled appointments at that clinic.

We will conduct three planned subgroup analyses:

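### Table 3's sample sizes and durations fit increases in appointment loss, not the reductions it labels; stated N is 15% to 52% too high, a conservative error

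*Combined protocol and SAP*

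**What the plan says.** Section 10 (Sample size and statistical analysis) takes a baseline appointment loss of 6.8% and sets the error rates: "Using standard parameters for Type 1 error (0.05, two-sided) and Type 2 error (0.20"). It names no formula. Table 3 then lists four effects, each labelled as a fall from 6.8%. The first reads "3% absolute difference (6.8% vs. 3.8"%; the others are falls to 4.8%, 5.8% and 5.4%, the last labelled a 20% relative difference. Stated totals (per group) are 2654 (1327), 5644 (2822), 21244 (10622) and 11112 (5556), with durations of 1.3, 2.7, 10.1 and 5.3 months. The section concludes: "Based on these calculations, a 6-month study will provide statistical power to detect a 20% relative difference in appointment loss".

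The text under Intervention delivery relies on this calculation. It expects "approximately 2100 eligible appointments per month", sets the study dates "to achieve the proposed sample size of approximately 13,000 appointments", and says: "The duration of the study will be dictated by the number of appointments necessary to detect an operationally significant reduction". Under Randomization, the plan adds that "we will limit the statistical analysis to the first randomized appointment during the project period".

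**The concern.** At a baseline of 6.8%, a fall needs fewer patients than a rise of the same absolute size, because the binomial variance shrinks as the rate moves towards zero. The stated N looks too large for falls, and the excess differs from row to row, so neither a higher power nor a fixed inflation factor would account for it.

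Table 3 is the only place where the plan sets effect sizes against N and months, and the duration is said to follow from it. If its figures do not follow from its inputs, the published justification of the trial's size cannot be reproduced. A second question is what N counts: the accrual rate and the 13,000 target count appointments, but only each member's first randomized appointment is analysed.

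**Working it through.** **Inputs.** Baseline p1 = 0.068 (Section 10). Table 1 supports it: (7612 × 9.2 + 7592 × 4.8 + 9283 × 6.5) / 24487 = 6.81%; and 175/2580 = 6.78%. Two-sided alpha 0.05 gives z = 1.960; Type 2 error 0.20 gives z = 0.842. Allocation is 1:1, since each total is twice the per-group N. Accrual is 2100 per month (Intervention delivery).

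**Formula (pooled, no continuity correction).** With p̄ = (p1 + p2)/2,

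n per group = [1.960 × √(2p̄(1 − p̄)) + 0.842 × √(p1(1 − p1) + p2(1 − p2))]² / (p1 − p2)².

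**Reproducing the plan's figures.** Enter the first row as a rise, p2 = 0.098. Then p̄ = 0.083, 2p̄(1 − p̄) = 0.152222 and the sum of variances is 0.151772, so n = (0.7647 + 0.3279)² / 0.03² = 1326.3, rounded up to 1327. That is the printed figure. The other rises give:

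| Increase from 6.8% to | n computed | Rounded up | Table 3 |
|---|---|---|---|
| 9.8% | 1326.3 | 1327 | 1327 |
| 8.8% | 2821.1 | 2822 | 2822 |
| 7.8% | 10621.7 | 10622 | 10622 |
| 8.2% | 5555.1 | 5556 | 5556 |

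**The labelled reductions.** For p2 = 0.038, p̄ = 0.053, 2p̄(1 − p̄) = 0.100382 and the sum of variances is 0.099932, so n = (0.6210 + 0.2660)² / 0.03² = 874.2, rounded up to 875. For all rows, per group:

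| Reduction to | Table 3 | Pooled | Excess | Continuity-corrected | Excess | Unpooled | Arcsine |
|---|---|---|---|---|---|---|---|
| 3.8% | 1327 | 875 | 52% | 940 | 41% | 872 | 859 |
| 4.8% | 2822 | 2143 | 32% | 2242 | 26% | 2141 | 2129 |
| 5.8% | 10622 | 9266 | 15% | 9465 | 12% | 9263 | 9253 |
| 5.4% | 5556 | 4587 | 21% | 4729 | 17% | 4584 | 4573 |

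An exact 20% cut is to 6.8% × 0.8 = 5.44%. It needs 4876 per group (5022 corrected), so the stated 5556 is 14% (11%) above.

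**Could another power level explain the table?** Power at the stated N for the labelled reductions is 93.2%, 89.5%, 85.1% and 86.9%. No single value fits.

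**Months.** Stated totals divided by 2100 give 1.26, 2.69, 10.12 and 5.29, which are the printed durations. With the pooled N: 1750/2100 = 0.8, 4286/2100 = 2.0, 18532/2100 = 8.8 and 9174/2100 = 4.4. With continuity correction: 0.9, 2.1, 9.0 and 4.5.

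**Effect on the design.** Six months at 2100 is 12,600 appointments, and the target is 13,000. Both exceed 9174 (for 5.4%) and 2 × 4876 = 9752 (for 5.44%). If every appointment were a first appointment, power for an exact 20% cut would be 89.0% at 6300 per group and 89.9% at 6500. Power stays at 80% as long as first appointments make up at least 9752/13000 = 75.0% to 9752/12600 = 77.4% of the total (77.3% to 79.7% with continuity correction). The documents do not give that share.

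**The case against.** The strongest reply is that nothing in the design turns on this. At the stated 5556 per group, power is 86.9% for 5.4% and 84.9% for an exact 20% cut, both above the planned 80%. The one conclusion drawn from Table 3 remains true, and surplus N costs participants little in a minimal-risk reminder study. All of that stands, and it limits the severity. It does not make the table right: four printed sample sizes and four durations do not follow from the stated inputs.

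A second reply is that the first-appointment point is separate from the arithmetic and speculative. The consent section estimates up to 15,000 eligible members, which gives no support for a high repeat rate, and the plan intends to monitor recruitment and adjust the randomization period. This stands in part. The 15,000 is an upper bound on members and not a share of first appointments, and the monitoring sentence does not say which unit is counted. The 75% to 77% threshold is therefore a condition to state, not a prediction that it will be missed.

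A third reply is that, if the number needed dictates the duration, the corrected N would imply 4.4 to 4.6 months rather than six. But 13,000 already exceeded the stated planning row of 11,112, so the plan carried a margin before any correction. Keeping it is reasonable.

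**Conclusion.** The concern holds. For the labelled reductions, Table 3 overstates N by 15% to 52% against the uncorrected pooled formula and by 12% to 41% against the continuity-corrected one; the unpooled and arcsine formulas do not reproduce it either. That the calculation was run for increases is an inference, since the plan does not show it, but an integer match in all four rows makes it very likely. The durations inherit the error.

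The error is conservative and changes no design decision. Six months still suffices for a 20% relative reduction, and a 1-point reduction still needs more than six months (8.8, not 10.1). This rests on the stated 6.8% baseline, 1:1 allocation, 2100 appointments per month, and enough of those being first appointments. The word conservative covers the formula error only, not the restriction to first appointments. It should be fixed because the published justification does not reproduce, not because the trial is underpowered.

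**What to change.** Replace the four rows of Table 3 and name the formula as the pooled two-proportion test without continuity correction:

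| Reduction | N total (per group) | Months at 2100 |
|---|---|---|
| 6.8% vs 3.8% | 1750 (875) | 0.8 |
| 6.8% vs 4.8% | 4286 (2143) | 2.0 |
| 6.8% vs 5.8% | 18532 (9266) | 8.8 |
| 6.8% vs 5.4% | 9174 (4587) | 4.4 |

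Add a footnote that an unrounded 20% cut, to 5.44%, needs 9752 (4876), or 4.6 months. If a continuity correction is preferred, use 1880 (940), 4484 (2242), 18930 (9465) and 9458 (4729), with 0.9, 2.1, 9.0 and 4.5 months and a footnote of 10044 (5022), 4.8 months.

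State that N counts analysed first appointments, so the months are minimums. Keep six months and 13,000, and describe the excess over the required N as margin. Keep the concluding sentence and add that it holds provided at least 9752 first appointments are analysed (10,044 with continuity correction). If power is quoted, label 89% to 90% for an exact 20% cut as an upper bound that assumes no repeat appointments.

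The cost is four table rows, a formula name, a footnote and short clarifying text, with no extra patients and no change to the duration or the target.

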Appendix 1. Study Variables

Variable	Use, comments, questions
Age	*
Sex	*
Race/ethnicity (white, Asian, black, Latino, Native American, unknown/other)	*
Marital status	
Employment	
Comorbidities	Quan index *
Mental health diagnoses	From MHRN list
Substance use diagnoses	From MHRN list
Number of address changes in last 12 months	New variable – created for [name]’s project
Number of telephone contact # changes in last 12 months	New variable – created for [name]’s project
Number of insurance plan changes in last 12 months	New variable – used by [name]
Clinic site	*Franklin, Lone Tree, Rock Creek
Day of week of appointment	
Exact time of day of appointment	
Health insurance type	*
Duration of enrollment in KPCO	
New member in KPCO	Individuals enrolled < 12 months will be defined as “new enrollees.” May conduct separate subgroup analysis for these individuals. [name] notes that several “segments” of new members have been defined for onboarding interventions.
Appointment lead time	* Exclude if <10 days
Number and rate of ED visits in prior 12 months	*
Number and rate of hospitalizations in prior 12 months	*
Number and rate of missed primary care appointments in prior 12 months	* We will consider various way of analyzing prior missed appointments: a) one or more b) relative risk for each additional missed visit

Number and rate of missed specialty care appointments in prior 12 months	*
Number and rate of missed GI endoscopy appointments in prior 12 months	
Appointment outcome (missed, kept, cancelled)	*
Bowel prep adequacy	Boston Bowel Prep scale (0-9 scale from GI smart set)
Applied for or received medical-financial assistance in last year	New variable – any IHR experience with this? [name] has a contact in KPNW who has extracted this variable UCDA also says that this is accessible.
Unpaid account balance	New variable – how to define?
Geo-located residence	We will use census tract as the primary unit of analysis
Distance from residence to clinic	
Picked up prep kit from KP Pharmacy	Prep kits provided by prescription only; may be picked up from non-KP pharmacies.

Notes:

1. include missing as a category for each variable
2. *= significant variable in prior predictive model(s) in primary care
3. For members with <12 months of enrollment, we will assess utilization from the beginning of enrollment to the date of the first scheduled primary care appointment.

Refs:

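### The weekly projection of kept visits and freed slots counts a change in cancellations twice, so it does not equal its stated target

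*Combined protocol and SAP*

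**What the plan says.** The Analytic plan in Section 10 describes an operational projection alongside the treatment comparison. Its target is the number of "additional kept visits and available appointments per week" that would follow from rolling out the better protocol. Its formula takes the mean visit count of a clinic and multiplies it "by the sum of the rate reduction in missed appointments and the rate increase in cancelled appointments at that clinic".

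Appendix 1 lists one outcome variable, "Appointment outcome (missed, kept, cancelled", with no split of cancellations by timing.

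Section 9 defines the primary outcome, appointment loss, as "the combined rate of prior day cancellations, same-day cancellations, and missed clinic appointments", and glosses the last component as no-shows. Prior-day and same-day cancellations count as losses because "it is difficult to schedule new procedures within this time frame".

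The word *missed* is not used in one sense. Section 9 limits it to no-shows, and the Analytic plan sets it beside late cancellations as a separate event ("after adjusting for predictors of missed appointments/late cancellations"). The sample size paragraph says that "approximately 2580 procedures/month were scheduled, and 175 were missed", which is the whole 6.8% loss. The projection sentence puts no timing limit on *cancelled*.

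**The concern.** The target has two parts: visits that are kept, and slots that are released early enough to be used again. A visit that moves out of *missed* must move into *kept* or *cancelled*, so the fall in missed already contains both parts. Adding the rise in cancelled counts the second part again.

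The formula is right only when cancellations do not change, and this intervention could well change them. The plan times its IVR-T reminders in business days because that is when the GI desk can cancel or reschedule. The added motivational messages might also turn would-be cancellers into attenders. Timely cancellations could therefore rise or fall.

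At stake is the number of slots gained per week at each clinic. The Dissemination section says that the findings go to the organizational sponsors. Because the terms are loose, two analysts could also report different numbers from the same data.

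**Working it through.** The documents give no numerical projection to reproduce, so the check is an accounting identity with illustrative sizes.

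**Inputs**
- Planned effect: 6.8% to 5.4% (Table 3), a fall of 1.4 points in appointment loss.
- Volume: "approximately 2100 eligible appointments per month" (Intervention delivery). At 4.348 weeks per month, 2100 / 4.348 = 483 per week. The sample size paragraph's 2580 per month less the plan's 10% exclusions is 2322, or 2322 / 4.348 = 534 per week.
- Table 1, 2018: N = 7612, 7592 and 9283; loss 9.2%, 4.8% and 6.5%; no-shows 2.5%, 1.2% and 1.2% (Franklin, Rock Creek, Lone Tree).

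**1. The identity in the plan's own categories.** Let d be the change, enhanced minus standard, in a share of all scheduled visits. The three shares sum to 1, so dKept + dCancelled = −dMissed.
- Target: dKept + dCancelled.
- Formula: −dMissed + dCancelled = dKept + 2 × dCancelled.

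The two agree only if dCancelled = 0.

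**2. How *missed* is used.** Weighted loss in Table 1 is (0.092 × 7612 + 0.048 × 7592 + 0.065 × 9283) / 24487 = 1668 / 24487 = 6.8%. Over an assumed 9.5 months that is about 176 per month, which matches the plan's 175. No-shows alone average 393 / 24487 = 1.6%, about 41 per month. Lone Tree's components add to 5.4% against a stated 6.5%. If the missing 1.1 points were all no-shows, the average would be 2.0%, about 52 per month. Either way, the 175 described as missed are all losses, not no-shows.

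**3. Split by timing.** Let N = no-show, L = late cancellation (prior-day or same-day), E = timely cancellation, K = kept. The changes sum to zero. A late cancellation is not an available slot by the plan's own reasoning, so the target is dK + dE = −(dN + dL), the fall in appointment loss. Two readings place every visit in exactly one Appendix 1 category:
- Reading 1 (missed = all loss, cancelled = timely): −(dN + dL) + dE. Error = dE.
- Reading 2 (missed = no-shows, cancelled = all cancellations): −dN + dL + dE. Error = dE + 2dL.

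| One visit moves from → to | Target | Reading 1 | Reading 2 |
|---|---|---|---|
| no-show → kept | 1 | 1 | 1 |
| no-show → timely | 1 | 2 | 2 |
| late → kept | 1 | 1 | −1 |
| late → timely | 1 | 2 | 0 |
| no-show → late | 0 | 0 | 2 |
| timely → kept | 0 | −1 | −1 |

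**4. Size under reading 1.** Let f be the share of averted losses that become timely cancellations. The documents give no value, so the whole range is shown. The formula gives target × (1 + f).

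| Visits/week | Target (slots/week) | f = 0 | f = 0.5 | f = 1 |
|---|---|---|---|---|
| 483 | 0.014 × 483 = 6.8 | 6.8 | 10.1 | 13.5 |
| 534 | 0.014 × 534 = 7.5 | 7.5 | 11.2 | 15.0 |

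If timely cancellations instead fell by 0.5 point (an assumption), the formula gives (1.4 − 0.5)% × 483 = 4.3 against a true 6.8.

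**5. Sign under reading 2 (assumed changes, 483 visits/week).**
- No-shows −0.4, late −1.0, timely 0: true gain 6.8; formula (0.4 − 1.0)% × 483 = −2.9.
- No-shows −0.5, late +0.5, timely 0: true gain 0; formula (0.5 + 0.5)% × 483 = 4.8.

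**The case against.** The strongest reply is that this is a descriptive figure with no test or threshold attached. The plan links implementation to whether the intervention works, not to this number. Clinic-specific effects are planned anyway, so anyone could multiply them by volume. That stands, and it limits the weight of the point. It does not make the formula correct.

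A second reply is that the method follows earlier IVR-T evaluations, as the Analytic plan says of its analyses in general. Precedent does not alter an identity, and here the outcome depends on when a cancellation is made.

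Three stronger readings are tempting, and the documents do not support them.
- *The double count occurs however the terms are read.* It does not. If *cancelled* meant late cancellations only and *missed* meant no-shows, a no-show that became a timely cancellation would count once. That reading fits available appointments poorly and has its own error: the formula becomes −dN + dL, which differs from the target by 2dL.
- *The projection always inflates the gain, or will show a loss.* Neither follows. Under reading 1 the error has the sign of dE, and it is zero if timely cancellations do not change. The negative result in step 5 needs reading 2 and an assumed split of the effect. Reading 2 is literally open, but it sits badly with the plan's own reason for counting late cancellations as losses.
- *Missed is undefined.* Section 9 does gloss it as no-shows. The fault is inconsistent use, and the contrary evidence is one clause in the sample size paragraph. What really has no definition in the formula is the timing of *cancelled*.

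**Conclusion.** The point holds, with limited scope: followed as written, the formula does not return its stated target whenever the counted cancellation rate changes. Under reading 1, the one closest to the plan's purpose, the overstatement at the planned effect runs from nothing to a doubling (6.8 to 13.5 slots a week on 483 visits), and a fall in timely cancellations produces an understatement. Under reading 2 the error can take either sign, because late cancellations that the primary outcome counts as losses are credited as gains.

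The identity assumes that the three Appendix 1 outcomes are exclusive shares of all scheduled visits. The sizes also assume that the 6.8% loss rate applies to that denominator; the documents do not say whether the N in Table 1 includes appointments cancelled earlier than the prior day. The share f is unknown, so no single figure for the error can be given.

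A reader might infer that the trial's main result is in doubt. It is not: the primary comparison, the sample size and the subgroup analyses do not use this formula.

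**What to change.** Replace the projection sentence with: average weekly eligible visits at the clinic × (appointment-loss rate under standard minus appointment-loss rate under enhanced), with a 95% confidence interval. If the two parts are wanted separately, report the change in kept visits and the change in cancellations made earlier than the prior day; they sum to that total.

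In the same sentence, use *no-show*, *late cancellation* (prior-day or same-day) and *timely cancellation* (earlier than the prior day) in place of *missed* and *cancelled*.

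The cost is one rewritten sentence and three definitions. No new data are needed, because the primary outcome already requires the timing of each cancellation.

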Operational leaders then proposed refinements to the IVR-T approach. We designed a 3-armed randomized trial in all KPCO primary care clinics comparing a single IVR-T reminder one day prior to a primary care visit, a single reminder 3 days prior to the visit, and two reminders, delivered both 1 and 3 days prior to the visit. In addition, we assessed the effect of the intervention in all primary care sites on visit satisfaction. This trial was conducted between October and December 2016. In this study, reminders both 1 and 3 days prior to a visit reduced missed appointments by 1.4% (absolute percentage) compared to a 3-day reminder, and by 0.9% compared to a 1-day reminder alone ($p<0.001$ for both comparisons). The effectiveness of 2 reminders was particularly strong in individuals who were at predicted high risk of missing appointments. For these individuals, 2 reminders reduced missed appointments by 4.5% and 3.7%, respectively. Based on these findings, 3-day and 1-day IVR-T reminders are now standard for all primary care visits in KPCO.

Clinical and operational leaders have now requested the IHR develop IVR-T interventions to reduce missed GI endoscopy procedures in KPCO. GI endoscopies (both upper and lower endoscopy) are performed at Franklin, Rock Creek, and Lone Tree facilities. GI clinic managers have tracked “appointment loss,” defined as prior-day cancellations, same-day cancellations, or missed visits since 2013. The trends over this period are shown in Table 1:

Table 1: Appointment Loss in GI Procedure Clinics, KPCO, 2013-2018

Site	2013	2014	2015	2016 (January-May)	2017	2018 (January- mid-October)
Franklin	8.7%	9.6%	8.8%	9.6%	x	Total = 9.2% No show – 2.5% Same-day cancel – 2.6% Prior day cancel – 4.1% N = 7612
Rock Creek	6.4%	6.4%	5.3%	5.9%	x	Total = 4.8% No show – 1.2% Same-day cancel – 1.2% Prior day cancel – 2.4% N = 7592
Lone Tree	6.0%	7.4%	5.2%	6.5%	x	Total = 6.5% No show – 1.2% Same-day cancel – 1.0% Prior day cancel – 3.2% N = 9283

These rates have been relatively constant over time. They represent substantial inefficiency for the KPCO system and prevent many members from receiving their procedure in a timely way. Each unfilled slot represents an estimated cost of about \$1200 to KPCO.

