1. We will develop a multivariable logistic regression model to predict appointment loss using approaches similar to prior IVR-T interventions. Clinic site will be included as a fixed effect. We will include linear and quadratic terms for continuous predictors and include both terms in the final model if statistically significant. Missing values for each predictor will be included as a separate category. Backward selection with Wald chi-square tests will guide the selection of predictors. The final prediction model will include an indicator variable for treatment group and all covariates with *p*-values <0.05. The discrimination of the model will be assessed with the *c*-statistic. We will use this prediction rule to stratify participants into risk quartiles and will assess the effectiveness of the intervention in each quartile.
2. We will assess the effectiveness of the intervention in each of the 3 participating clinics, after adjusting for predictors of missed appointments/late cancellations, to provide preliminary information on site-level factors that may modify intervention effectiveness.
3. We will analyze the effectiveness of the intervention in the subgroup of individuals who schedule their endoscopies \leq 7 days prior to the procedure, since these individuals will receive no reminders under the standard protocol.

Human subjects

The standard reminder protocol includes a text message that “rolls over” to an IVR automated phone if the text cannot be delivered. The GI Clinic has received permission from the KPCO Compliance Office to send emails to the private email addresses of KPCO members.

Study Risks: This study utilizes current standard protocols for contacting KPCO members and data collected during the course of routine clinical care to improve efficiencies in the delivery and quality of care for patients. Therefore, the primary risk of this study is the potential for loss of confidentiality and privacy of a member, through a loss or inappropriate disclosure of study data. There are no known risks to investigators or staff.

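### Risk quartiles in planned subgroup analysis 1 are formed from a model containing the treatment term, so an effective intervention unbalances the arms within each quartile and hides much of its own effect

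*Combined protocol and SAP*

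**What the plan says.** Section 10, planned subgroup analysis 1, builds a logistic model for appointment loss by backward selection, with clinic site as a fixed effect. "The final prediction model will include an indicator variable for treatment group and all covariates with" p-values under 0.05. The text continues: "We will use this prediction rule to stratify participants into risk quartiles and will assess the effectiveness of the intervention in each quartile".

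Nothing in this item fixes the treatment term at one value for scoring, cuts quartiles separately by arm, or adjusts the within-quartile comparisons. Adjustment is written for the overall effect in the analytic plan ("We will assess the effectiveness of the intervention across the 3 participating clinics, after adjusting for predictors of missed appointments/late cancellations") and for the by-clinic analysis, item 2 ("We will assess the effectiveness of the intervention in each of the 3 participating clinics, after adjusting for predictors of missed appointments/late cancellations"). Item 3, on members who schedule within 7 days, states none.

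**The concern.** A subgroup variable in a randomized trial should not depend on the assigned arm. Here it does. If the intervention works, its coefficient is negative and every enhanced member's predicted risk drops. An enhanced member then needs worse covariates than a standard member to land in the same quartile, and the balance given by randomization is lost inside every quartile.

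This is the plan's analysis of effect by predicted risk. The background reports from the earlier primary-care trial: "The effectiveness of 2 reminders was particularly strong in individuals who were at predicted high risk of missing appointments". The intervention section adds: "Selective live reminders for members at high risk of missed appointments will be assessed in Step 3 of this project". The quartile results are therefore a natural input to that later step, although the plan does not say that the step depends on them. Understated effects, or small spurious harm in lower-risk members, would misdirect that discussion.

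**Working it through.** The plan gives no figure for the quartile analysis, so there is none to reproduce; its rates serve as inputs.

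**Inputs**
- Standard-arm loss 6.8% (section 10, Table 3). Enhanced-arm loss 6.8% × 0.80 = 5.44%, printed as 5.4%. Equal groups, as in Table 3.
- N: "the proposed sample size of approximately 13,000 appointments". Also 11,112, the Table 3 total for this effect, because "we will limit the statistical analysis to the first randomized appointment during the project period" and the analysed number may be below 13,000.
- Spread of the risk score: assumed. The documents give no c-statistic for this model; the published rule in the literature review had 0.75 and 0.70. I used SDs of 0.551, 0.757 and 0.989 on the log-odds scale (c = 0.65, 0.70 and 0.75 for a normal score).

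**Model.** logit P(loss) = a + z + bT, where z is the covariate score and T = 1 for enhanced. Choose a so that the mean of expit(a + z) is 0.068, and b so that the mean of expit(a + b + z) is 0.0544. For a normal score with SD 0.757: a = -2.856, b = -0.247, odds ratio 0.781.

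**Scoring as written.** Standard members are ranked on z and enhanced members on z - 0.247. The pooled cut-points are -0.641, -0.123 and 0.394. A standard member enters the top quartile at z = 0.394, an enhanced member only at z = 0.394 + 0.247 = 0.641.

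| Quartile | Standard share of quartile | Untreated risk, standard | Untreated risk, enhanced | Enhanced, observed | Apparent reduction | True reduction | Lost |
|---|---|---|---|---|---|---|---|
| 1 | 40% | 2.05% | 2.49% | 1.96% | 0.09 | 0.49 | 81% |
| 2 | 47% | 3.87% | 4.85% | 3.83% | 0.03 | 0.92 | 96% |
| 3 | 53% | 6.20% | 7.73% | 6.15% | 0.05 | 1.43 | 96% |
| 4 | 60% | 12.76% | 14.82% | 12.02% | 0.74 | 2.61 | 72% |

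Reductions are in percentage points, taken before rounding. The true reduction uses common cut-points on covariate risk. In the top quartile, treatment lowers the enhanced members' risk by 14.82 - 12.02 = 2.80 points, but they start 14.82 - 12.76 = 2.06 points higher, which leaves 0.74.

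**Other score shapes** (constant odds ratio, all three SDs; last column at SD 0.757)

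| Shape | Quartile 1 lost | Quartiles 2-3 lost | Quartile 4 lost | Quartile 4 reduction, as written vs true |
|---|---|---|---|---|
| Normal | 80-82% | 96% | 71-73% | 0.74 vs 2.61 |
| Uniform | 54-57% | 100% | 45-47% | 1.41 vs 2.60 |
| Right-skewed gamma | 58-59% | 97-98% | 91% | 0.26 vs 2.82 |
| Left-skewed gamma | 94-95% | 97-98% | 52-53% | 1.06 vs 2.23 |

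A more extreme exponential shape widens quartile 4 to 43-100% and quartile 1 to 46-100%.

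**Simulated trials** (one risk covariate plus nine noise covariates, fitted logistic model, two-sided 0.05)
- At N = 13,000 the top quartile is significant for enhanced in 1-20% of trials as written, against 53-74% with treatment set to standard for scoring. At N = 11,112: 1-16% against 43-65%.
- Setting treatment to standard, or cutting quartiles within arm, brings the quartile means at N = 13,000 within 0.09 points of truth.
- Under a null effect the quartile means as written are within 0.03 points of zero.

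**Benefit concentrated in high-risk members.** The background gives 4.5/1.4 = 3.2 and 3.7/0.9 = 4.1 times the overall effect in high-risk members, but not what share of members was high-risk. Two readings, with 12 shape-by-SD cases each and the same overall effect:
- Top quarter at 3 times: quartiles 1 and 2 fall below zero in 12 of 12 cases and quartile 3 in 11 of 12 (values -0.01 to -0.99; true reductions 0.17 to 0.82). Quartile 4 reads 1.16 to 2.98 against a true 4.08.
- Top tenth at 3.2 times: quartiles 2 and 3 fall below zero in 11 of 12 cases and quartile 1 in 3 of 12, none beyond -0.39. Quartile 4 reads 0.17 to 2.44 against a true 2.66 to 3.16.

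**The case against.** The bias needs three things together: scores using the actual arm, pooled cut-points and unadjusted contrasts. The plan says its methods follow earlier reminder trials, and those may have scored on covariates alone or adjusted within quartiles. Silence on adjustment in item 1 may be uneven drafting, since item 3 is silent too. The analysis is secondary, and the overall result is untouched.

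Much of this is fair. Within-arm cut-points would largely remove the bias. So would covariate adjustment: in simulation it brought the top-quartile mean log odds ratio within 0.007 of the true value (-0.240 to -0.278). It does not restore all power, because the arms stay unequal in size within quartiles. With a left-skewed score the top quartile is significant in 36-50% of trials, against 53-58% when scoring is also fixed. But neither remedy is written for this analysis, and a general reference to earlier methods does not override a specific rule whose plain antecedent is the model containing treatment.

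Two limits also stand. The spurious harm in lower quartiles is small: the largest value, -0.99 points, has a standard error of 0.81 at N = 13,000 (0.99/0.81 = 1.2), so a typical trial would not show significant harm. And the direction is not universal once the odds ratio varies. With a left-skewed score at SD 0.551 and 4.1 times the effect in the top tenth, quartile 4 is overstated (3.37 against 3.03), while quartiles 1 to 3 read -0.25, -0.49 and -0.64.

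**Conclusion.** The concern holds: the analysis is wrong as written and should be fixed. Under a constant odds ratio every quartile effect is pulled towards zero, whatever the score shape. The size of the loss rests on the assumed spread and shape of the risk score, on 1:1 allocation and on the Table 3 effect. If benefit is concentrated in high-risk members, the lower quartiles can show slight apparent harm where there is slight benefit, and the top quartile is usually understated. The damage is confined to this subgroup analysis.

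**What to change.** Add a sentence to planned subgroup analysis 1, for example: *Risk scores will use pre-randomization covariates and clinic site only (the treatment term may stay in the fitted model but is set to standard for every member when predicting), and one set of quartile cut-points will apply to both arms.* This removes the bias.

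Also state that the within-quartile effects carry the covariate adjustment already written for the overall and by-clinic analyses. Once scoring is fixed, that is for consistency rather than validity.

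The cost is one sentence in the plan and one line of code. Conduct, sample size and data collection do not change.
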